##### **3.3.1.2 *Main analytical approach***

The time to response will be assessed on the subgroup of participants who have achieved confirmed OR and summarized using descriptive statistics.

The analyses of DOR and PFS will be based on estimands 2 and 3 introduced in [Section 1.2.1](#) and defined according to the following attributes:

- The endpoints are DOR and PFS.
- The treatment condition is SAR444245 in combination (refer to [Table 1](#)).

- The analysis population for DOR corresponds to all participants from the efficacy population who achieve either confirmed PR or confirmed CR.
- The analysis population for PFS corresponds to all participants from the efficacy population.
- Intercurrent events:
  - The new anticancer therapy IE will be handled with the **hypothetical** strategy: DOR and PFS will be assessed based on tumor assessments had a new anticancer therapy not being taken. DOR and PFS will be assessed based on tumor assessments up to the time of new anticancer therapy.
  - The early IMP discontinuation IE will be handled with the **treatment policy** strategy: DOR and PFS will be assessed based on tumor assessments irrespective of IMP discontinuation.
  - Two or more consecutive missing/unevaluable tumor assessments immediately before documented progression or death will be handled with the **hypothetical** strategy: DOR and PFS will be assessed based on tumor assessments had two consecutive tumor assessments not been missed immediately before documented progression or death.
- Population-level summary will include the Kaplan Meier estimate of DOR and PFS and corresponding CI at specified time points. CIs for KM estimates will be estimated using the Kaplan Meier method and log-log approach based on a normal approximation following the Greenwood's formula. The quantiles of DOR and PFS and corresponding CI from Kaplan Meier method will also be provided. CI will be constructed using a log-log transformation of the survival function and the methods of Brookmeyer and Crowley. In the absence of disease progression or death before the cut-off date, DOR and PFS will be censored as indicated in [Table 6](#).

**Table 6 - Censoring rules for DOR and PFS**

Situation	Date of progression or censoring	Outcome	Category
No baseline tumor assessments a	Date of first treatment intake	Censored	No baseline tumor assessments
No evaluable b post-baseline tumor assessments a	Date of first treatment intake	Censored	No evaluable post-baseline tumor assessments
Progression documented at or between scheduled visits	Date of the first tumor assessment documenting progression	Event	Documented progression
New anticancer treatment before documented progression	Date of the last evaluable tumor assessment before new treatment	Censored	New anticancer treatment
Death prior to the first planned post-baseline tumor assessment a	Date of death	Event	Death

Situation	Date of progression or censoring	Outcome	Category
Death at or between scheduled visits	Date of death	Event	Death
Death or documented progression immediately after two c or more missed or non-evaluable tumor assessments	Date of the last evaluable tumor assessment documenting no progression	Censored	Death or progression after two or more missed/unevaluable tumor assessments
Alive and no documented progression	Date of the last evaluable tumor assessment	Censored	Alive without documented progression

[figure not shown]
*a* Not applicable for DOR.  
*b* Evaluable TA means an evaluation different from non-evaluable.  
*c* Two consecutive tumor assessments are considered as missed/non-evaluable if the duration between two consecutive tumor assessments done (non-missing) and evaluable is strictly longer than 20 weeks.

[figure not shown]
The clinical benefit rate will be summarized using the same estimand as for the primary endpoint.

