**Table 1 - Overview of study cohorts**

Substudy	Cohort	Study intervention	Disease
01	A	SAR444245 + pembrolizumab	2-3L ESCC - Regardless of CPS Post-PD1/PDL1
02	B1	SAR444245 + pembrolizumab	1-3L GC/GEJ non-MSI-H CPS $\geq 1$ PD-1/PD-L1 Naïve
02	B2	SAR444245 + pembrolizumab	1-3L GC/GEJ non-MSI-H CPS $< 1$ PD-1/PD-L1 Naïve
02	B3	SAR444245 + pembrolizumab	2-4L GC/GEJ non-MSI-H - Regardless of CPS Post-PD1/PDL1
03	C	SAR444245 + pembrolizumab	2-3L post PD1/PDL1 HCC
04	D1	SAR444245 + pembrolizumab	3-6L mCRC non-MSI-H Any RAS
04	D2	SAR444245 + cetuximab	3-6L mCRC non-MSI-H RASwt

ESCC: esophageal squamous cell carcinoma; CPS: combined positive score; GC: gastric cancer; GEJ: gastro-esophageal junction adenocarcinoma, HCC: hepatocellular carcinoma; 1-3L: first to third line; 2-4L: second- to fourth-line; 2-3L: second to third line; 3-6L: third to sixth line; mCRC: metastatic colorectal cancer; MSI-H: high-level microsatellite instability; PD1/PDL1: programmed cell death 1 or programmed cell death-ligand 1; RASwt: RAS wild-type RECIST: response evaluation criteria in solid tumors;

After a screening period of up to 28 days, participants will receive treatment until progressive disease (PD), unacceptable adverse event (AE) or other full permanent discontinuation criteria (described in Section 7 of the master protocol) or completion of Cycle 35 (if applicable).

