**Table 4 - Summary of primary estimand for main endpoints**

Endpoint Category (estimand)	Estimands			
	Endpoint	Population	Intercurrent event(s) (IE) handling strategy	Population-level summary (Analysis and missing data handling)
Primary objective: To determine the antitumor activity of SAR444245 in combination with other anticancer therapies				
Primary endpoint (estimand 1)	Objective Response (OR) (confirmed CR or PR)	Efficacy	
 
While not initiating new anti-cancer therapy (NAT)
 
Regardless of early IMP discontinuation (treatment policy strategy)
 
	ORR, defined as the percentage of the participants with objective response (CR or PR) as best overall response. Confidence interval will be calculated using Clopper Pearson methods.
Secondary objective: To assess other indicators of antitumor activity of SAR444245 in combination with other anticancer therapies				
Secondary endpoint (estimand 2)	DOR	Responders from efficacy population	
 
Had NAT not been initiated (hypothetical strategy)
 
Regardless of early IMP discontinuation (treatment policy strategy)
 
Had two or more consecutive tumor assessments not been missed/unevaluable immediately before documented progression or death (hypothetical strategy)
 
	
The Kaplan Meier estimate and corresponding confidence interval of DOR at specified time points.
 
The quantiles of DOR and corresponding confidence interval from Kaplan Meier method.

Secondary endpoint (estimand 3)	PFS	Efficacy	
 
Had NAT not been initiated (hypothetical strategy)
 
Regardless of early IMP discontinuation (treatment policy strategy)
 
Had two or more consecutive tumor assessments not been missed/unevaluable immediately before documented progression or death (hypothetical strategy)
 
	
The Kaplan Meier estimate and corresponding confidence interval of PFS at specified time points.
 
The quantiles of PFS and corresponding confidence interval from Kaplan Meier method.

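### Table 6 gives two opposite PFS outcomes, with no precedence, for a death between about week 9 and week 20 without an evaluable post-baseline scan, and footnote c cannot time a gap that ends in death

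*SAP*

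**What the plan says.** Section 3.3.1.1 counts any death as a PFS event. Section 3.3.1.2 introduces Table 6 as the censoring rules for participants with neither progression nor death by the cut-off. The rows of Table 6 that matter here are:

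- "No evaluable post-baseline tumor assessments": censored, at "Date of first treatment intake". PFS only. The row does not require the participant to be alive.
- "Death prior to the first planned post-baseline tumor assessment": event at death. PFS only.
- "Death at or between scheduled visits": event at death. The row does not require an earlier evaluable scan.
- "Death or documented progression immediately after two" or more missed or non-evaluable assessments: censored at the last evaluable assessment showing no progression.

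Footnote c treats two assessments as missed if "the duration between two consecutive tumor assessments done (non-missing) and evaluable is strictly longer than 20 weeks". In Table 4, Estimand 3 sets PFS events aside on only two grounds: new anticancer therapy, and "Had two or more consecutive tumor assessments not been missed/unevaluable immediately before documented progression or death (hypothetical strategy"). Table 5 keeps participants with no evaluable post-baseline scan in the efficacy population if they stopped treatment permanently, and PFS is analysed in that population.

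**The concern.** Two rows with opposite outcomes apply to the same participant, and nothing says which one wins. A programmer would have to choose, possibly with the data in view. The participants concerned are likely to be among those who did worst: never successfully scanned, then dead. Scoring them as censored on day 1 would remove known deaths from the PFS curve, which neither the endpoint definition nor the estimand allows after a single missed scan.

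Footnote c has a related fault. Its row covers both progression and death, yet its rule needs an evaluable scan at each end of the gap. A death is not a scan, so the rule cannot be applied to it as written. It also leaves open whether the gap may start at a baseline scan taken before the first dose.

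**Working it through.** The SAP gives no PFS estimate, so there is no figure to reproduce. The check has a logical part and an arithmetic part.

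**1. Scan schedule (inferred).** Section 3.3.1.1 states a scan at 27 weeks with a 7-day window. Scans every 9 weeks fit this (3 × 9 = 27) and also fit the limit in footnote c (2 × 9 + 2 × 1 = 20 weeks).

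**2. Which deaths are in dispute.** For participants with no evaluable post-baseline scan and no new therapy:

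| Time of death | Rows that fit | Result |
|---|---|---|
| Before about week 9 | no-scan row; early-death row | The dedicated early-death row makes it an event |
| About week 9 to week 20 | no-scan row; death at or between visits | Censored at day 1, or event at death: unresolved |
| After about week 20 | as above, plus the row for two or more missed scans | Arguably censored under the estimand, but footnote c does not define the gap |

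**3. Which outcome the SAP supports.** The PFS definition counts any death. The sentence before Table 6 ties censoring to the absence of progression or death. Estimand 3 has no exception for one missed scan. All three point to an event.

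**4. Effect if the no-scan row were applied.** Inputs: N = 40 (Section 4); k, the number of disputed deaths, is an assumption because the SAP gives no value.

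Take a time after all k deaths, with no other earlier censoring and m participants still event-free. Scored as events, S = m/40. Censored at day 1, S = m/(40-k). The ratio is 40/(40-k):

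| k | 40/(40-k) |
|---|---|
| 1 | 1.026 |
| 2 | 1.053 |
| 4 | 1.111 |
| 6 | 1.176 |
| 8 | 1.250 |

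For example, with k = 4 and m = 12: 12/40 = 30.0% against 12/36 = 33.3%.

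Before the k deaths the direction reverses. If m' of the other 40-k participants are event-free, scoring as events gives (m'+k)/40 and censoring gives m'/(40-k), which cannot be larger. With k = 4 and m' = 27: 31/40 = 77.5% against 27/36 = 75.0%.

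**5. Simulation.** Assumptions: 2,000 cohorts of 40 per setting; exponential PFS for the other participants; disputed deaths uniform over weeks 9 to 20; cut-off at 78 weeks. Mean of the estimated median PFS for k = 4, in weeks:

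| Median of the others | Censored at day 1 | Event at death | Difference |
|---|---|---|---|
| 26 | 25.3 | 21.9 | +3.4 |
| 18 | 17.7 | 16.6 | +1.1 |
| 13 | 12.8 | 13.2 | -0.4 |
| 9 | 8.8 | 9.9 | -1.1 |

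At 26 weeks, with the others' median at 18 weeks and k = 4, PFS is 36.9% against 33.2%, a ratio of 1.111 as in step 4.

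**6. Footnote c and baseline.** Section 1.1 allows dosing "After a screening period of up to 28 days". If the gap could start at a baseline scan on day -28, progression at week 18 after one missed scan would give 18 + 4 = 22 weeks, above the limit and so counted as two missed. With progression at week 18 this needs a baseline scan more than 14 days before dosing (18 + 2 = 20, which does not exceed 20).

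**The case against.** The strongest reply is that the natural reading is already the right one. Any death is a PFS event, the sentence before Table 6 confines censoring to participants without progression or death, and the no-scan row does not mention death. The only row that censors a death names that exception openly, and the estimand matches it. This stands as evidence of intent. It does not settle the table, for two reasons. Table 6 does censor some deaths, so the introductory sentence does not govern every row. And the separate event row for deaths before the first planned scan suggests that the no-scan row would otherwise capture deaths, which invites the reading that later ones are captured.

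A reader might go further and infer three things that the SAP does not support.

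- That Table 6 removes early deaths. The earliest deaths have their own event row; only the window from about week 9 to week 20 is open.
- That the plan inflates PFS. This would need the no-scan row to prevail, and it holds only for landmarks after the disputed deaths. Earlier landmarks fall, and the median can fall too.
- That progression after one missed scan will be censored at a baseline scan before time zero. The SAP does not say that the gap starts at baseline, and a baseline scan hardly documents absence of progression. The example also rests on an inferred schedule and an early baseline scan.

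Nor is it inconsistent that these participants are non-responders for ORR; the two endpoints differ.

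**Conclusion.** The point holds as a conflict between two rows without stated precedence, together with a footnote that cannot be applied to deaths. The text favours the event, so the error is possible rather than prescribed. If the no-scan row were used, PFS at landmarks after the disputed deaths would be too high by 5% relative for k = 2 and 11% for k = 4, assuming no other earlier censoring. The size rests on k, which is assumed, and the limits of the window rest on the inferred 9-week schedule. The direction for the median depends on where it lies relative to these deaths.

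The consequence is limited. PFS is a secondary endpoint, its intervals are descriptive, nothing is tested, and the futility rule uses ORR. The correction is still worth making, because the rule as written can give a result that the SAP's own estimand excludes, and it is cheap to repair before PFS is programmed.

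**What to change.** 1. Limit the rows for no baseline assessment and for no evaluable post-baseline assessment to participants without documented progression and without a death that counts as an event.
2. State that a death within 20 weeks of first IMP with no evaluable post-baseline assessment is an event at the date of death, unless new anticancer therapy started earlier. In that case the new-therapy row takes precedence, with censoring at first intake if there is no post-baseline scan. Without this exception the new wording would clash with the new-therapy row and with the estimand.
3. In footnote c, measure the gap from the later of first IMP and the last evaluable assessment to the date of progression or death. Where there is no evaluable post-baseline assessment and the gap exceeds 20 weeks, censor at first intake. Progression at week 18 after one missed scan then has a gap of 18 weeks and remains an event.

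The cost is a few lines in Table 6 and no new data. Late-landmark PFS may be slightly less favourable than it would be under the no-scan row.

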### 3.3.2 Supportive secondary endpoint(s)

Not applicable.

## 3.4 EXPLORATORY ENDPOINT(S) ANALYSIS

### 3.5 MULTIPLICITY ISSUES

No formal testing will be performed. Therefore, no multiplicity issues need to be addressed.

### 3.6 SAFETY ANALYSES

The analysis of the safety variables will be descriptive, and no testing is planned.

#### 3.6.1 Extent of exposure

If applicable, summaries will be provided by trial impact (disruption) due to COVID-19.

##### 3.6.1.1 *Overall exposure*

The dose information will be assessed by the following variables:

- Overall number of cycles started, defined by the number of cycles in which at least one dose of any study interventions is administered.
- Duration of IMP exposure (in months) is defined as (Last day of exposure – first day of exposure +1)/30.4375.
- The first day of exposure is defined as the first administration date with non-zero dose for at least one of the IMP (refer to [Table 1](#)).

The last day of exposure is the day before the theoretical date of the next administration (after the last administration), defined as the maximum between:

- The last administration date + 20 for SAR444245,
- The last administration date + 20 for pembrolizumab or the last administration date + 6 for cetuximab according to the cohort (refer to [Table 1](#)).

The total number of cycles started and number of cycles started by participants will be summarized by category. The duration of overall exposure will be summarized quantitatively.

The following variable will be computed to describe overall dose modification (cycle delay):

- Cycle delay: A cycle is deemed as delayed if the start date of the current cycle - theoretical duration of a cycle - start date of the previous cycle is  $\geq 4$  days. Cycle delay is not defined for the first cycle.

Cycle delay will be analyzed at the participant (with number of participants used as denominator) and cycle (with number of cycles used as denominator) levels, as follows:

- Number (%) of participants with at least 1 cycle delayed
  - Number (%) of participants with a cycle delayed between 4 and 7 days (using maximum delay across all cycles)
  - Number (%) of participants with a cycle delayed more than 7 days (using maximum delay across all cycles)
- Number (%) of cycles delayed
  - Number (%) of cycles delayed between 4 and 7 days
  - Number (%) of cycles delayed more than 7 days

### **3.6.1.2 SAR444245 exposure**

The dose information will be assessed by the following:

- Total number of cycles started per participant
- Duration of SAR444245 exposure (in months) is defined by (date of last administration of SAR444245 + 21 – date of first administration of SAR444245)/30.4375.
- Actual dose ( $\mu\text{g}/\text{kg}$ )
- Cumulative dose ( $\mu\text{g}/\text{kg}$ ): the cumulative dose is the sum of all actual doses of SAR444245, given from first to last administration
- Actual dose intensity (ADI in  $\mu\text{g}/\text{kg}/\text{week}$ ): defined as the cumulative dose divided by the duration of SAR444245 exposure (in weeks)
- Planned dose intensity (PDI in  $\mu\text{g}/\text{kg}/\text{week}$ ): corresponds to the planned dose at C1D1 divided by the theoretical cycle duration expressed in weeks (i.e. 3 weeks)
- Relative dose intensity (RDI, in %):  $100 \times \frac{\text{ADI } (\mu\text{g}/\text{kg}/\text{week})}{\text{PDI } (\mu\text{g}/\text{kg}/\text{week})}$

The total number of cycles started, number of cycles started by participant will be summarized by category. Duration of SAR444245 exposure, cumulative dose, ADI and RDI will be summarized quantitatively and by category if relevant.

The following variables will be derived to describe dose modifications and dose interruptions:

- Dose reduction: The first administration will not be counted as a dose reduction. For the second and subsequent SAR444245 administrations, dose reduction will be determined using the dose level intervals provided in [Table 7](#), by comparing the current dose level to the previous dose level. If the current dose level is below the dose level interval of the previous dose administration, then the current dose level is considered reduced.

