**Table 7 - SAR444245 dose reduction criteria**

Actual dose level	Dose level interval
8 µg/kg	
16 µg/kg	
24 µg/kg	

- Dose omission is defined as a dose not administered at the scheduled visit.
- Dose interruption: A dose will be considered as interrupted if SAR444245 administration is stopped during an infusion regardless of whether it is restarted or not.

Dose modifications and dose interruptions will be analyzed by participant and dose as follows:

- **Participant** (number of participants treated will be used as denominator)
  - Number (%) of participants with at least 1 dose modification
    - Number (%) of participants with at least 1 dose reduction
    - Number (%) of participants with at least 1 dose omission
  - Number (%) of participants with at least 1 dose interruption
    - Number (%) of participants with at least 1 dose interrupted and restarted
    - Number (%) of participants with at least 1 dose interrupted and not restarted
  - Number (%) of participants with at least 2 dose interruptions
- **Dose** (number of doses started will be used as denominator)
  - Number of doses
  - Number (%) of dose interruptions
  - Number (%) of doses interrupted and re-started
  - Number (%) of doses interrupted and not re-started
  - Number (%) of doses interrupted more than once,
  - Number (%) of doses interrupted at 1st dose, 2nd dose, subsequent doses,
  - Time from dose start to first interruption in minutes summarized as a continuous variable and by category.

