**Table 8 - Cetuximab dose reduction criteria**

Actual dose level	Dose level interval
250 mg/m 	> 225 mg/m 
Dose level -1 (200 mg/m  )	>175 mg/m  and ≤225 mg/m 
Dose level -2 (150 mg/m  )	>0 mg/m  and ≤175 mg/m 

- Dose omission is defined as a dose not administered at the scheduled visit.
- Dose interruption: A dose will be considered as interrupted if cetuximab administration is stopped during an infusion regardless of whether the infusion is restarted or not.

Dose modifications and dose interruptions will be analyzed by participant as follows:

- Participant** (number of participants treated will be used as denominator)
  - Number (%) of participants with at least 1 dose modification
    - Number (%) of participants with at least 1 dose reduction
    - Number (%) of participants with at least 1 dose omission
  - Number (%) of participants with at least 1 dose interruption
    - Number (%) of participants with at least 1 dose interrupted and re-started
    - Number (%) of participants with at least 1 dose interrupted and not re-started
  - Number (%) of participants with at least 2 dose interruptions

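### On its natural reading, the dose-reduction rule can count an incomplete infusion as a dose reduction, and a truncated exempt infusion can hide a real later one

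*SAP*

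**What the plan says.** SAP section 3.6.1.2 derives SAR444245 dose reductions "by comparing the current dose level to the previous dose level", and then states: "If the current dose level is below the dose level interval of the previous dose administration, then the current dose level is considered reduced". The only exemption is "The first administration will not be counted as a dose reduction". Section 3.6.1.4 words the cetuximab rule the same way but exempts the first two administrations.

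The first column of Tables 7 and 8 is headed "Actual dose level". Table 8 gives three cetuximab intervals: above 225 mg/m² (250 level), above 175 up to 225 (200 level), and above 0 up to 175 (150 level). The Table 7 intervals are blank in the text at hand and are not treated as an omission.

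Interruption is defined separately. For SAR444245: "A dose will be considered as interrupted if SAR444245 administration is stopped during an infusion regardless of whether it is restarted or not". For cetuximab: "A dose will be considered as interrupted if cetuximab administration is stopped during an infusion regardless of whether the infusion is restarted or not". For both drugs it is listed beside dose modification, not under it, with its own line for infusions that were not resumed (for SAR444245, "Number (%) of participants with at least 1 dose interrupted and not restarted"). Table 10 likewise has one row for adverse events leading to interruption and another for those leading to modification.

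**The concern.** The SAP keeps two things apart: lowering the dose, and stopping an infusion before it is complete. The derivation of reduction does not keep them apart if the dose level is what the participant received. A stopped infusion delivers less than the previous one and can fall below its interval. The truncated amount then becomes the comparator for the next administration, so a deliberate step down may look like no change or an increase.

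Incomplete infusions are foreseen: the exposed population in Table 5 accepts an incomplete dose, and section 3.6.2 plans detailed summaries of infusion reactions. A reader will take the percentage with a dose reduction to mean deliberate lowering. It could partly reflect stopped infusions, and it could omit some genuine reductions.

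**Working it through.** The SAP states no figure on this point, so there is nothing to reproduce. The check applies the written rule to example sequences, taking the dose level as the dose delivered.

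**Rule.** For each non-exempt administration, flag a reduction if the current dose is not above the lower bound of the interval containing the previous dose. A participant counts if at least one administration is flagged.

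**Cetuximab.** Lower bounds from Table 8 are 225, 175 and 0 mg/m². The first two administrations are exempt. The first dose of 400 is illustrative and not in the SAP; it does not affect the results, because the third administration is compared only with the second.

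| Doses delivered (mg/m²) | Decisive comparison | Participant counted? |
|---|---|---|
| 400, 250, 250, 125 (stopped), 250 | 125 against >225 | Yes, no deliberate reduction |
| 400, 250, 250, 225 (stopped), 250 | 225 against >225 | Yes, no deliberate reduction |
| 400, 250, 250, 230 (stopped), 250 | 230 against >225 | No |
| 400, 150, 150, 75 (stopped), 150 | 75 against >0 | No |
| 400, 250, 200, 200 | 200 against >225 | Yes, correctly |
| 400, 125 (stopped), 200, 200 | 200 against >0 | No, real step to 200 missed |

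The last row assumes that 250 was intended at the second administration. As a share of the intended dose, the flag appears at 225/250 = 90% or less after a 250-level dose, and at 175/200 = 87.5% or less after a 200-level dose. After a 150-level dose it cannot appear, since no delivered amount is below an interval starting just above 0.

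**SAR444245.** The first administration is exempt. As the intervals are not visible, three sets of lower bounds for the 24, 16 and 8 µg/kg levels were assumed: 20/12/0, 21.6/14.4/0 and 16/8/0. The flag after a 24-level dose then appears at 20/24 = 83%, 21.6/24 = 90% or 16/24 = 67% delivered, or less. All three sets give the same results:

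- 24, 24, 12 (stopped), 24: flagged at the 12, with no deliberate reduction.
- 24, 24, 23, 24: not flagged.
- 24, 16, 16: flagged, correctly.
- 10 (first dose of an intended 24, stopped), 16, 16: never flagged, so the step to 16 is missed.
- 24, 10 (stopped), 16, 16: flagged at the 10 but not at the 16. The participant is still counted.

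The last two sequences show when masking changes the output. Reductions are summarised only as participants with at least one. A truncated dose that is itself tested has usually already put the participant in the count. The count falls mainly when the truncated dose is an exempt one.

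**Size.** Section 4 plans about 40 participants per cohort. One misclassified participant moves the reduction percentage by 1/40 = 2.5 points, upward for a false reduction and downward for a missed one.

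**The case against.** The strongest objection is that the rule speaks of a dose level, which the SAP does not define, and that section 3.6.1.2 lists the actual dose as a separate variable. The levels in Tables 7 and 8 are nominal steps and could be prescribed ones. If the level is the prescribed one, neither effect arises. This stands as a possibility, but the text points the other way: the column heading refers to actual levels, the lowest Table 8 interval takes in any partial dose, and the SAP says planned where it means planned. The SAR444245 planned dose intensity, for example, "corresponds to the planned dose at C1D1 divided by the theoretical cycle duration expressed in weeks". The reduction rule has no such word.

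A reader might infer more than the SAP supports:

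- That every infusion stopped and not restarted is counted as a reduction. It is not: exempt administrations, nearly complete infusions and truncations after a lowest-level cetuximab dose are not flagged.
- That any truncated dose hides later reductions from the output. At participant level this is mainly confined to exempt doses.
- That listing one event under two headings is an error in itself. The SAP never declares the lines mutually exclusive, and unresumed infusions stay visible on their own line. The problem is that the reduction line would contain events that were not reductions.
- That the reduction rate is the plan's leading tolerability measure. The SAP ranks none, and also reports relative dose intensity, omissions, interruptions, cycle delays and adverse events leading to changes in treatment.

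**Conclusion.** The point holds in a limited form. With dose level read as the dose delivered, the visible Table 8 bounds are enough to show a false reduction (250, then 125 stopped) and a missed one (400, 125 stopped, 200, 200). The same can occur for SAR444245, at thresholds that the text at hand does not show. This is a misclassifying rule rather than a mere lack of detail.

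Its reach is small. It affects the descriptive percentages of participants with a dose reduction or a dose modification for these two drugs. Cumulative dose, actual and relative dose intensity and the efficacy analyses do not use the flag. The net error cannot be derived from the documents, because they do not give the frequency of incomplete infusions, the amounts delivered, or the overlap with true reductions. Only the conversion of 2.5 points per misclassified participant in a cohort of 40 is fixed. The correction is worth making because it is cheap and the SAP itself intends the two concepts to be separate.

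**What to change.** In sections 3.6.1.2 and 3.6.1.4, define the dose level in the reduction rule as the level planned (prescribed) for that administration, for both the current dose and its comparator. Report incomplete delivery under dose interruption. For cetuximab, the SAP already sums planned doses over the doses started to obtain planned dose intensity, so the information appears to be available. For SAR444245 the SAP names a planned dose only at C1D1, so the sponsor should check whether one is recorded for each administration.

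If it is not, the delivered amount of an incomplete infusion, restarted or not, should be neither the value tested nor the comparator. The comparator should be the last completed administration or, for SAR444245 when there is none, the planned C1D1 dose. The SAP should state the downside: a deliberately lowered dose that is then stopped would not be counted as a reduction until a later completed dose.

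The cost is a few sentences in the SAP and a small programming change. Interruption and restart status are already needed for the planned tables. Whether restarted infusions were completed must also be identifiable. The design and the other analyses are unchanged.
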